**FCM**

*OR*

**Ferrous Sulfate**

## 7.2 Reporting of Adverse Events

Adverse experiences will be elicited by nonspecific questions such as "Have you noticed any problems?" Participants will be encouraged to report adverse events at their onset. Any adverse experience spontaneously reported by, elicited from the participant, or observed by the physician or study staff, shall be recorded on the appropriate Adverse Event page of the eCRF. The investigator will record the date and time of onset, severity, the relationship to study medication, the date and time of resolution (or the fact that the event is still continuing), the action taken, and the outcome of the adverse experience on the Adverse Event page of the eCRF. Whenever possible, the investigator should group together, into a single term, signs and symptoms which constitute a single diagnosis. For example, cough, rhinitis and sneezing might be grouped together as "upper respiratory infection."

The local investigator is responsible for reporting SAEs to their local IRB/ Ethics Committee based on local reporting guidelines (which may be different than those specified in this protocol). The responsible investigator should institute appropriate diagnostic and therapeutic measures and keep the participant under observation for as long as is medically indicated.

## 8.0 STATISTICS

All hypothesis tests and confidence intervals will be two-sided. No correction for multiple testing will be applied amongst the secondary endpoints. Except where otherwise noted, the statistical model on which inference is based will include terms for randomization strata.

Continuous variables will be summarized in terms of the number of observations, mean, standard deviation, median, Q1, Q3, minimum and maximum. Other descriptive statistics (e.g., coefficient of variation) may be reported when appropriate. Categorical variables will be summarized using frequency counts and percentages.

Generally, data will be summarized by nominal visit. However, data from both unscheduled and scheduled will be used for determination of last observed value, and in worst- or best-case changes and/or shifts from baseline. Assessment windows will not be defined for the purpose of classifying measurements obtained outside scheduled assessment times.

A complete description of the statistical analyses and methods will be available in a Statistical Analysis Plan (SAP), which will be finalized before the database is locked.

## **8.1 Stratification/Randomization**

Participants who meet the inclusion/exclusion criteria will be randomized on Day 0 to FCM or oral iron in a 1:1 ratio. The randomization will be stratified by hemoglobin (<10, ≥10 g/dL) and age (1 to <12 and ≥12 to 17 years).

## **8.2 Analysis Populations**

### **Intent-to-Treat Population**

The Intent-to-Treat (ITT) population will comprise all randomized participants. Participants will be evaluated according to the treatment to which they were randomized. Any participant who receives a treatment randomization number will be considered to have been randomized.

### **Modified Intent-to-Treat Population**

The modified Intent-to-Treat (mITT) population will comprise all participated in the ITT population who receive at least one dose of study drug, have a baseline hemoglobin measurement, and at least one corresponding post-baseline measurement. Participants will be evaluated according to the treatment to which they were randomized. The primary population for the assessing efficacy will be the mITT population.

### **Safety Population**

The safety population will consist of all participants in the ITT population who received at least one dose of study drug. Participants will be evaluated according to treatment received. This population will be used for assessing safety.

### **Pharmacokinetics Population**

The Pharmacokinetics (PK) population will consist of all participants in the Safety population with at least one measurable concentration of FCM.

### **8.3 Disposition and Baseline Characteristics**

The number of participants in each investigative site will be summarized. The number of participants who are screened, randomized, treated, prematurely discontinued, and complete the study will be summarized.

The clinical team will identify deviations and the deviations will be identified in the database. Participants with clinically important protocol deviations will be summarized.

Demographics and baseline characteristics will be summarized using descriptive statistics or frequency counts.

### **8.4 Endpoints and Definitions**

#### **8.4.1 Primary Endpoint**

The primary endpoint is the change in hemoglobin from baseline to day 35. The change in hemoglobin from baseline to day 35 will be analyzed using parametric analysis of covariance (ANCOVA). The model will include terms for the randomization strata (hemoglobin and age categories), baseline hemoglobin, as well as treatment group. Baseline hemoglobin will be defined as the last hemoglobin obtained before randomization.

The primary endpoint will be analyzed for the mITT population.

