### 6.3 Treatment Phase (Day 0 to Day 35)

#### 6.3.1 Day 0 Visit

The following will be obtained and/or completed before contacting IRT for randomization:

For all participants:

- Verify all inclusion and exclusion criteria (See section 4.2.1 and 4.2.2)
- Physical exam
- Review concomitant medications (to include ESA and IBD stability, if applicable).

A participant who develops a bacterial infection during the screening phase should be discontinued and treated appropriately. These participants may be re-screened, one time, once the enrolling physician deems the participant would qualify for study entry. The participant will need to re-sign a new consent / assent form and all screening procedures in section 6.2 will need to be repeated.

After verifying the eligibility of the participant, the IRT system will then be contacted by a study team member. Randomization will be stratified by hemoglobin (<10, ≥10 g/dL) and age (1 to <12 and ≥12 to 17 years), and randomized in a 1:1 ratio to either Group A (FCM at 15 mg/kg to a maximum single dose of 750 mg on Days 0 and 7 for a maximum total dose of 1500 mg) or Group B (Ferrous sulfate, dose and regimen dependent upon age and weight, twice daily for 28 days).

After a randomization number has been obtained, the **first dose** of oral ferrous sulfate will be administered in the clinic according to the following: infants and children (1 to <4 years of age) will receive ferrous sulfate drops; children (≥4 to <12 years of age) will receive ferrous sulfate elixir or ferrous sulfate tablets; and adolescents (≥12 to 17 years of age) will receive ferrous sulfate tablets.

A sufficient quantity of doses for a 7-day period will be dispensed to the parent or guardian of the participant. The parent or guardian of the participant will be responsible for the administration of two daily doses of oral ferrous sulfate to the participant.

After assignment of the treatment group, the following will occur:

All participant's (prior to study drug administration/dispensing, if applicable) on Day 0:

- Blood samples for central lab hematology, chemistries, and iron indices (Group

- A participants will have an additional blood sample for PK prior to dosing)
- Vital signs: temperature, sitting heart rate and blood pressure
- Weight

Group A:

- Blood samples for PK immediately (within 5 minutes) post-dose and 60 minutes post dose.
- Verify amount of single FCM dose (15mg/kg up to a maximum single dose of 750 mg).

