### **8.5.4 Clinical Laboratory Findings**

Clinical laboratory variables will be presented in two ways. First, the mean change from baseline to each scheduled visit will be summarized. Second, the number and percent of participants with treatment-emergent PCS laboratory values will be tabulated. Treatment-emergent PCS laboratory tests are those in which the baseline value is normal and post-baseline value is abnormal (i.e., meets Grade III or Grade IV toxicity criteria from the NCI-CTC Version 5 or higher). Baseline will be defined as the last value obtained before randomization.

No formal statistical tests will be performed.

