## 2.3 DEFINITIONS AND CONVENTIONS FOR DATA HANDLING

### 2.3.1 Baseline Definition

For evaluations collected at multiple time points, the baseline will be defined as the last value obtained before randomization.

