### 2.3.4 Handling of Missing Data

A participant who withdraws from the study for any reason will be included in the analyses regardless of time on study. Methods for handling withdrawals and missing data will be specific to each endpoint to be analyzed. Missing data will not be imputed for descriptive statistical summaries in safety or efficacy.

For statistical inferential (models) analyses, missing data will be imputed using last observation carried forward (LOCF) method for hemoglobin and other efficacy endpoints. e.g. for primary endpoint, hemoglobin, when Day 35 data is missing (subject has discontinued before Day 35, or measurement not taken at Day 35 though subject was not discontinued), Day 28 result will be carried forward. If the post-baseline value of the first scheduled visit is missing, the worst value obtained from the same time point of all subjects in ITT population will be used for both treatment groups. The worst value is defined as the lowest value for hemoglobin, ferritin, TSAT and reticulocyte hemoglobin content.

Supportive analyses will assess the impact of missing values on inferences based on primary efficacy endpoints and missing data will be handled by using missing at random (MAR) in

mixed effect model repeat measurement (MMRM) model. The observed case will also be applied for primary analysis.

Dates missing the day or both day and month of the year will adhere to the following conventions to classify TEAE and to classify prior/concomitant medications.

- A medication with a completely missing start date will be considered a prior medication. A medication with a completely missing stop date will be considered a concomitant medication.
- If complete AE onset date is missing and AE end date is on or after the first dose date then it will be counted as a treatment emergent AE (TEAE) for the study. If complete AE onset date is missing and AE end date is before the first dose date then it will be counted as a not treatment emergent AE (TEAE) for the study.
- If an AE or a medication has a partial missing start or stop date, the following rules will be used for imputation:
  - If year is present but month and day are missing, impute start date as January 1 of that year or first dose date if the year is the same as the year of first dose date and impute stop date as December 31 of that year.

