#### **MMRM Analysis of Change in hemoglobin from baseline to Day 35:**

A mixed model repeated measures (MMRM) model will be conducted to provide an analysis under the assumption that data are missing at random (MAR). The MMRM model will include changes in hemoglobin from baseline to each post-baseline visit as the dependent variables; and treatment group, visit and treatment group by visit interaction as fixed effects; and subjects within treatment group as random effects; and baseline hemoglobin (<10, ≥10 g/dL) and age (1 to <12 and ≥12 to 17 years) as covariate. An unstructured covariance matrix will be used to allow for unequal variances between visits. If the model does not converge with unstructured variance – covariance matrix, then the Toeplitz, first-order autoregressive, compound symmetric, variance components structures will be tried and the covariance structure will be decided based on model convergence status and the AKaike information criterion. The Kenward-Roger approximation will be used to calculate the denominator of degrees of freedom for the fixed effect. If the interaction term is not significant, it will be dropped from the model. No imputation of missing data other than that inherent in the MMRM model will be performed. P-values to test treatment effect on Day 35 will be reported. Point estimates and associated 95% confidence interval will be reported.

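### Baseline is the last value before randomization, but Day 0 blood is drawn after assignment and before dosing, so a pre-treatment sample can count as post-baseline

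*Protocol*

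**What the plan says.** The baseline rule is the same wherever it appears.

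- Protocol 8.4.1, for the primary endpoint: "Baseline hemoglobin will be defined as the last hemoglobin obtained before randomization".
- Protocol 8.5.4, for laboratory findings: "Baseline will be defined as the last value obtained before randomization".
- SAP 2.3.1, in general: "For evaluations collected at multiple time points, the baseline will be defined as the last value obtained before randomization". SAP 6.1.1 repeats it for hemoglobin and SAP 7 for laboratory data.

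Protocol 6.3.1 fixes the order of events on Day 0. The first list opens "The following will be obtained and/or completed before contacting IRT for randomization" and contains the eligibility check, the physical exam and the medication review, with no blood draw. Hematology, chemistry and iron indices come later, under "After assignment of the treatment group, the following will occur", and before study drug is given or dispensed.

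Several rules depend on what is post-baseline:

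- SAP 2.3.4 uses LOCF for inferential analyses, with a fallback: "If the post-baseline value of the first scheduled visit is missing, the worst value obtained from the same time point of all subjects" (the lowest value in the ITT population) is used instead.
- The hemoglobin MMRM in SAP 6.1.1 takes "changes in hemoglobin from baseline to each post-baseline visit as the dependent variables".
- SAP 7.3 counts potentially clinically significant (PCS) laboratory values at any post-baseline visit, tabulates shifts from baseline, and gives a time course of serum phosphate for FCM participants with a normal baseline.
- The mITT definition (protocol 8.2, SAP 2.2.2) requires a post-baseline measurement.

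**The concern.** The definition and the visit procedure do not meet. The only scheduled hemoglobin before randomization is the screening one, so the Day 0 pre-dose sample, the natural baseline, is not baseline under the text. Neither document says whether that sample is baseline, post-baseline or neither. Two programmers could both follow the text and produce different tables.

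Three things are at stake. Abnormalities present before any drug could be attributed to treatment. A participant with no on-treatment hemoglobin could enter the primary analysis with a pre-treatment value standing in for Day 35. Within-arm changes would also include about a week in which supplemental iron is not allowed (protocol 4.2).

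**Working it through.** **1. Which value is baseline.** Screening is at Day -7 ± 1 (protocol 6.2.1; the schedule of events prints -7 + 1), so the screening sample is about 6 to 8 days old at randomization. No other hemoglobin is scheduled before the IRT call. An unscheduled one would displace it. The amendment log explains how this arose: before Amendment 1 the Day 0 draw preceded the IRT call. The amendment moved the draw and kept the baseline rule.

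**2. The plan's own figure.** Per arm, n = 2(1.960 + 1.282)² × 1.16² / 1.0² = 28.3, so 29 (58 in total) by the normal approximation. By the noncentral t, power is 89.7% at 29 per arm and 90.7% at 30. The stated 60 reproduces and does not depend on the baseline question.

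**3. Effect on the primary contrast, complete cases.** ANCOVA was simulated with 30 per arm, a true difference of 1.0 g/dL, the hemoglobin stratum and the baseline covariate. Assumptions not in the documents: true hemoglobin mean 9.5 and SD 1.0, Day 35 residual SD 1.1, within-person SD 0.2 to 0.6, and a screening-to-Day 0 drift of 0 or -0.3 g/dL.

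| | Screening baseline | Day 0 baseline |
|---|---|---|
| Treatment estimate | 0.995–1.006 | 0.995–1.005 |
| Standard error | 0.292–0.318 | 0.292–0.312 |
| Mean change over both arms, drift -0.3 | 1.21–1.26 | 1.50 |

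The largest power difference is 88.2% - 86.7% = 1.5 points. The contrast does not move; the within-arm change does.

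**4. How far screening and Day 0 can differ.** Inputs are the screening means (SD) in protocol Table 1, 9.2 (1.20) and 9.5 (0.81), selection on screening hemoglobin below 11 g/dL, and an assumed within-subject SD of 0.2 to 0.5. The SD of the difference is about √2 × 0.2 = 0.28, rising to 0.70 at 0.5 (√2 × 0.5 = 0.71 before selection). Regression to the mean adds 0.004 to 0.03 g/dL in both arms. About 6% to 24% of participants change hemoglobin category (<10, ≥10).

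**5. A participant with Day 0 blood and nothing later.** If Day 0 is post-baseline, it is carried to Day 35 and the change is near zero. If post-baseline starts at Day 7, the worst-value rule applies. Suppose the Day 7 spread resembles screening. Among 72 participants the lowest value then lies about 1.9 to 2.7 g/dL below the mean. One such participant moves a 36-person arm mean by 1.9/36 = 0.05 to 2.7/36 = 0.08 g/dL. An assumed imbalance of three moves the unadjusted contrast by 3 × 1.9/36 = 0.16 to 3 × 2.7/36 = 0.23, against a planned 1.0. This is the gap between two readings of the same text.

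**6. Laboratory tables.** Take a normal screening value and a Grade 3 or 4 value in pre-dose Day 0 blood. The participant is in the PCS denominator (normal baseline, a post-baseline assessment) and in the numerator. For phosphate, if days are counted as in SAP 2.3.2, a low pre-dose value falls on study day 0 + 1 = 1, the day of first dose, and reads as very early onset under FCM. The documents give no basis for a frequency.

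**7. MMRM and mITT.** Day 0 would be an outcome visit at which the true treatment effect is zero. It could dilute a pooled estimate if the interaction is dropped as SAP 6.1.1 allows; the size was not computed. A pre-drug sample would satisfy the mITT requirement.

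**The case against.** A baseline fixed before assignment is a defensible choice in an open-label trial, and the plan applies it consistently. Protocol Table 1 reports the sponsor's Phase II results as change from screening, and section 3.2 describes the same hemoglobin figures as change from baseline, so a screening baseline has precedent here. The week before dosing is common to both arms and cancels in the contrast. All of this stands.

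It can also be said that neither document calls Day 0 post-baseline. Both name Days 7, 14, 28 and 35 as the return visits after randomization, and the LOCF example carries Day 28 forward, so Day 7 is the natural first post-baseline visit. That is probably the intention. But the definition as written puts pre-dose Day 0 blood after baseline, and no sentence takes it out again.

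The smaller consequences are rightly discounted. The SAP moves efficacy to ITT and leaves mITT for post hoc sensitivity analyses, and the MMRM is supportive.

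A reader might infer that the primary treatment effect is biased. The documents do not support that: the rule is the same in both randomized arms, and step 3 shows no shift. A reader might also infer that worst-value imputation is the right handling for someone with no on-treatment hemoglobin. Nothing in the plan establishes that. It is a harsher single imputation, and step 5 shows only that the text leaves the choice open.

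**Conclusion.** The mismatch is real and follows from the text. It does not threaten the complete-case primary contrast, and the precision gain from a Day 0 baseline is small.

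Its practical weight lies in three places. Treatment-emergent PCS counts and the phosphate time course can include pre-dose findings. LOCF can carry a pre-treatment hemoglobin to Day 35. Within-arm changes include a pre-treatment week without supplemental iron: with an assumed drift of -0.3 g/dL, the mean change reads 1.21 to 1.26 instead of 1.50. The mITT and MMRM consequences are minor.

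The sizes rest on assumed within-subject variation and drift, on a Day 7 spread like that at screening, and on an assumed number of participants without on-treatment data. The existence of the ambiguity rests on none of these. It is a cheap improvement worth making before database lock.

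**What to change.** In protocol 8.4.1 and 8.5.4 and SAP 2.3.1, 6.1.1 and 7:

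- Define baseline as the last value before the first dose of study drug: Day 0 pre-dose, or screening if that is missing. For participants randomized but never dosed, use the last value before randomization.
- State that post-baseline visits start at Day 7 for LOCF, the worst-value rule, mITT, MMRM and the laboratory PCS, shift and phosphate tables.
- Keep the hemoglobin stratum as recorded in the IRT for the ANCOVA strata term and the hemoglobin subgroup. Day 0 central-laboratory blood is drawn after assignment, so the IRT stratum presumably rests on the screening value.

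The cost is wording in both documents; the sample is already scheduled. There are two small downsides. Baseline would be taken after an open-label assignment, although it is an objective central-laboratory value drawn before dosing. And about 6% to 24% of participants would have a Day 0 hemoglobin category different from their IRT stratum, under the assumed within-subject SD of 0.2 to 0.5 g/dL.

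If the sponsor prefers the pre-randomization baseline for efficacy, the minimum change is one sentence: pre-dose Day 0 values are neither post-baseline nor treatment-emergent.

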#### **Subgroup analyses**

The change in hemoglobin from baseline to day 35 will be summarized separately for the following subgroups:

- Cause of IDA: IBD, not IBD
- CKD, not CKD
- Baseline hemoglobin : <10, ≥10 g/dL
- Age: 1 to <12, ≥12 to 17 years

Estimates of treatment effect together with 95% confidence intervals will be displayed graphically.

Subgroup analyses will be conducted for the mITT population.

#### **8.4.2 Secondary Endpoints**

Secondary efficacy endpoints include:

- Change in ferritin from baseline to Day 35
- Change in TSAT from baseline to Day 35
- Changes from baseline to in hemoglobin, ferritin, TSAT, and reticulocyte hemoglobin content.
- Pharmacokinetic assessments, including  $C_{max}$ ,  $T_{max}$ ,  $AUC_{0-time}$  last measured concentration,  $AUC_{0-infinity}$ ,  $T_{1/2}$ , MRT, Cl,  $V_D$ ,  $V_{Dc}$ ,  $V_{Dss}$ , and  $V_{Darea}$ . These assessments will be

based on a population pharmacokinetic analysis using data from this study and 1VIT13036.

Continuous efficacy endpoints will be analyzed using ANCOVA as described for the primary endpoint. Binary efficacy variables will be analyzed using stratified Cochran-Mantel-Haenszel chi-square tests.

All secondary efficacy endpoints will be analyzed for the mITT population.

Details of analyses for these endpoints will be outlined in the SAP.

### **Pharmacokinetics and Pharmacodynamics (PK/PD) Endpoints**

The PK parameters will be calculated by standard non-compartmental analysis according to current working practices and using WinNonlin®. All calculations of non-compartmental parameters will be based on actual sampling times. The actual sampling times and doses will be used for the analysis. The PK parameters will be calculated with and without adjustment for baseline. All derived PK parameters will be listed. The following summary statistics will be calculated: n, mean, standard deviation [SD], coefficient of variation (CV), median, minimum, and maximum, along with geometric mean, geometric mean SD, geometric percent coefficient of variation [%CV], and 95% CIs around the geometric mean. For  $T_{max}$ , only n, median, minimum and maximum will be presented.

In addition, nonlinear mixed effects modelling will be used derive population PK parameters and/or models. The influence of various covariates (e.g., age, weight, sex, race) on the variability will be examined. Further details will be provided in the SAP.

The relationship between FCM exposure and clinical outcome may be explored graphically. If appropriate, a relationship may be established between FCM exposure and effect or any special interest adverse events. Further details will be provided in the SAP.

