### 3.3 Rationale for Sparse Pharmacokinetic Sampling:

Population-based PK/PD modelling describing the time course of total serum iron (TSI) concentrations and the relationship between TSI and changes of hemoglobin following a single dose of intravenous FCM in pediatric subjects with IDA has been performed using intensively sampled data from Study 1VIT13036. It is proposed to supplement this initial modelling with additional sparsely sampled PK data from this study. Based on the anticipated visit duration on the 2 FCM administration days in this study, the following sparse PK sampling scheme is proposed: pre-dose, immediately (within 5 minutes) post-infusion and 60 minutes post-dose on Days 0 and 7, on which subjects will receive 15 mg/kg (up to a maximum dose of 750 mg). This pragmatic approach, which minimizes the number of blood draws compared to a full PK profile, is expected to facilitate exposure-response analysis for the proposed FCM regimen.

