### **6.3.6 Pharmacokinetic Sampling**

Blood samples will be collected for PK assessment pre-dose, immediately (within 5 minutes) post-dose, and 60 minutes post-dose for participants receiving FCM on Days 0 and 7. Blood samples should be taken at approximately the same time of day (within 1 hour) on Day 7 as Day 0.

The pharmacokinetic parameters to be analyzed in this study are as follows: the maximum serum concentration ( $C_{max}$ ) and the time at which  $C_{max}$  occurs ( $T_{max}$ ), the area under the

serum concentration-time curve from time zero to the last sampling time with a quantifiable concentration ( $AUC_{0-\text{time last measured concentration}}$ ), the extrapolated area under the serum concentration-time curve from time zero to infinity ( $AUC_{0-\text{infinity}}$ ), and the half-life ( $T_{1/2}$ ). The secondary parameters were the mean residence time (MRT), the apparent serum clearance (Cl), and the apparent volume of distribution ( $V_D$ ), which includes the initial volume of distribution following the injection ( $V_{Dc}$ ), the volume of distribution at the steady state ( $V_{Dss}$ ), and the volume of distribution at the final elimination ( $V_{Darea}$ ).

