#### 1.2.2 Secondary Efficacy Endpoint(s)

- Change in ferritin from baseline to Day 35
- Change in transferrin saturation (TSAT) from baseline to Day 35
- Changes from baseline in hemoglobin, ferritin, TSAT, and reticulocyte hemoglobin content (CHr) throughout the study.
- Pharmacokinetic assessments, including  $C_{max}$ ,  $T_{max}$ ,  $T_{1/2}$ , MRT, Cl,  $V_D$ ,  $V_{DC}$ ,  $V_{DSS}$ ,  $V_{Darea}$ ,  $AUC_{0-\infty}$  and  $AUC_{0-\text{time last measured concentration}}$ . These assessments will be based on a population pharmacokinetic analysis using data from this study and the 1VIT13036 study.

The analysis of PK assessments is not addressed in this SAP.

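### The protocol orders non-compartmental estimates of half-life, AUC to infinity, MRT, clearance, VDss and VDarea that its sparse sampling cannot support, and that conflict with the population PK basis it gives for the same parameters

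*Protocol*

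**What the plan says.** Protocol Section 8.4.2 lists Cmax, Tmax, two AUCs, T1/2, MRT, Cl and the distribution volumes as a secondary endpoint, and states that the assessments will be "based on a population pharmacokinetic analysis using data from this study and 1VIT13036". SAP Section 1.2.2 repeats this: "These assessments will be based on a population pharmacokinetic analysis using data from this study and the 1VIT13036 study".

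The PK/PD subsection that follows in the same protocol section gives a different method: "The PK parameters will be calculated by standard non-compartmental analysis according to current working practices and using WinNonlin". It adds: "All calculations of non-compartmental parameters will be based on actual sampling times". All derived parameters are to be listed and summarised, with geometric means and 95% confidence intervals among the statistics. The model comes afterwards: "In addition, nonlinear mixed effects modelling will be used derive population PK parameters and/or models". Further modelling and exposure-response detail is deferred to the SAP, but SAP Section 1 puts pharmacokinetic analyses out of its scope.

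Sampling on the two dosing days (Day 0 and Day 7) is set in protocol Section 6.3.6: "Blood samples will be collected for PK assessment pre-dose, immediately (within 5 minutes) post-dose, and 60 minutes post-dose for participants receiving FCM". Protocol Section 3.3 gives the purpose: "It is proposed to supplement this initial modelling with additional sparsely sampled PK data from this study". It contrasts this scheme with a full PK profile.

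**The concern.** Two passages in one section give different methods for the same named parameters, and the sampling suits only one of them. The non-compartmental instruction is unconditional. It is not limited to parameters that can be read from the observed concentrations. It also cannot be read as non-compartmental analysis of model-predicted curves, because it is tied to actual sampling times.

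An analyst following the PK/PD subsection would have to list and summarise paediatric half-lives, clearances and volumes resting on a slope through two points less than an hour apart. Those values would stand beside the population model's values, and nothing in the text says which set prevails. The subsection also does not say which exposure estimate would feed any exposure-response work.

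**Working it through.** **Inputs from the documents.** Post-dose PK samples per dose: two, within 5 minutes and at 60 minutes (protocol Sections 3.3, 3.4 and 6.3.6). Later PK sample after the first dose: the Day 7 pre-dose draw (Section 6.3.2), at 7 × 24 = 168 h. No later PK draw is scheduled after the second dose.

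**Assumed inputs.** The documents state no half-life and no assay error. I take half-lives of 6 to 16 h and per-sample errors (CV) of 5% and 10%, with mono-exponential decline from the end of dosing and the first sample at 5 minutes. The plan states no figure to reproduce.

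**Which parameters need the terminal slope, λz.**
- T1/2 = ln 2/λz
- AUC0-infinity = AUC0-last + Clast/λz
- Cl = dose/AUC0-infinity
- MRT uses areas extrapolated to infinity
- VDss = Cl × MRT
- VDarea = Cl/λz

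Cmax, Tmax and AUC0-last do not need it. A crude VDc, dose over the first post-dose concentration, does not either.

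**Precision of a two-point slope.** Two points fit a log-linear line exactly, leaving 0 residual degrees of freedom. With k = ln 2/T1/2 and a gap d = 55/60 = 0.917 h:
- fall between samples = 1 − exp(−k·d)
- share of AUC0-infinity beyond 1 h = exp(−k × 1 h)
- P(slope zero or negative) = Φ(−k·d/(√2·σ)), where σ = √ln(1 + CV²)
- √2·σ = 0.0707 at 5% and 0.1411 at 10%

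Worked case at 6 h: k = 0.1155 per hour and k·d = 0.1059. The fall is 1 − exp(−0.1059) = 10.0%, and the share beyond 1 h is exp(−0.1155) = 89%. P = Φ(−0.1059/0.0707) = 7% at 5% error, and Φ(−0.1059/0.1411) = 23% at 10%.

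| Assumed T1/2 | Fall, 5 to 60 min | AUC0-infinity beyond 1 h | P(slope ≤ 0), 5% error | P(slope ≤ 0), 10% error |
|---|---|---|---|---|
| 6 h | 10.0% | 89% | 7% | 23% |
| 8 h | 7.6% | 92% | 13% | 29% |
| 16 h | 3.9% | 96% | 29% | 39% |

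If the first sample is drawn exactly at the end of dosing (d = 1 h), the last two columns run from 5% to 27% and from 21% to 38%, so the conclusion does not depend on the 5 minutes.

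A positive slope does not mean a usable half-life. With a true half-life of 12 h and 10% error, simulation puts the middle 80% of the estimable values at about 2.4 to 26 h.

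**Does the Day 7 pre-dose sample help?** The drug fraction left at 168 h is exp(−168k), which is 0.0007 at 16 h and smaller at shorter half-lives. Under these assumptions the sample measures essentially endogenous iron. Taking that level as 1% to 10% of peak (also assumed), an unadjusted log-linear fit through 5 minutes, 60 minutes and 168 h returns about 25 to 50 h, whether the true value is 6 or 16 h. A linear trapezoid to 168 h gives 3.5 times the true drug AUC at 16 h and 8.7 times at 6 h, even after baseline subtraction. The serum iron measured with the Day 14, 28 and 35 iron indices comes at least 7 days after a dose and does not fill the gap either.

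**The case against.** The strongest reply is that the endpoint already has a sound basis. Section 8.4.2 and SAP Section 1.2.2 both name the pooled population analysis, and Section 3.3 designs the sampling for it. The amendment log fits this reading: the non-compartmental paragraph entered with Amendment 1, and the population PK sentence was added in Amendment 2 as a clarification. The older paragraph looks left over rather than chosen. This stands. A reader might infer that the PK endpoint cannot be delivered, or that the PK/PD subsection is the only text governing it. The documents do not support either inference, because the population basis is equally current.

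A second reply is that standard practice might record these parameters as not estimable, giving blanks rather than bad numbers. The plan gives no slope-acceptance rule, so this is possible. It limits how literally to take the percentages above, but it does not rescue the instruction. Either the required summaries are empty, or they cover only the profiles where noise happened to give a positive slope.

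Third, the percentages rest on assumed half-lives and errors. That is so, and they are illustrative. The absence of PK samples between 60 minutes and 168 h after the first dose is fact.

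Fourth, a reader might extend the point to every listed parameter or to all the volumes. That goes too far, since Cmax, Tmax, AUC0-last and a crude VDc do not need the terminal slope. Nor do the documents attach a hypothesis test, dosing decision or safety rule to the PK values, and the exposure-response work is optional.

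**Conclusion.** The concern holds for six parameters: T1/2, AUC0-infinity, MRT, Cl, VDss and VDarea. The PK/PD subsection requires non-compartmental values that two first-hour samples cannot validly supply, and it conflicts with the population PK basis stated in the same protocol section and in the SAP.

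Under the assumed 6 to 16 h half-life, 89% to 96% of AUC0-infinity would be extrapolated. Adding an assumed 5% to 10% per-sample error, 7% to 39% of two-point slopes would yield no half-life at all. The exact figures move with these assumptions. The lack of terminal-phase sampling does not.

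The harm is a mandated second set of unreliable estimates and confidence intervals alongside the model-based ones. The primary endpoint is untouched, and the PK endpoint remains achievable through the population model. The text should be reconciled before the PK analysis.

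**What to change.** Amend the PK/PD subsection of protocol Section 8.4.2 in three ways.

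1. State that T1/2, AUC0-infinity, MRT, Cl, VDss and VDarea come only from the population PK model, as individual post hoc estimates with shrinkage reported.
2. Limit direct summaries to the observed pre-dose, end-of-dose and 60-minute concentrations, including observed Cmax and Tmax, with and without baseline correction. AUC0-last and VDc would then follow the population basis already given in Section 8.4.2.
3. Replace the references to the SAP for PK detail with a named PK analysis plan, since the SAP excludes PK.

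The cost is one paragraph of wording and a cross-reference. No blood draws are added, and the work of producing the non-compartmental tables for these parameters falls away.
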